8.2.3.2. Sensitivity Analysis using Multiple Imputation

Missing CRR assessments at Week 37 will be imputed using MI methods based on similar subjects with non-missing values at assumption of missing at random (MAR) and missing not at random (MNAR). First, missing values of composite CRR elements, UPCR and eGFR will be imputed separately, then missing CRR will be imputed based on the composite definitions in Section 3.2.1.

To implement multiple imputation of missing values of UPCR and eGFR, there will be two imputation steps carried out for each of these measures. First step, a Markov Chain Monte Carlo (MCMC) model imputes all intermediate missing values. Second step, a monotone regression model imputes remaining monotone missing values.

In the first step, the Markov Chain Monte Carlo (MCMC) models will be used with a single chain to impute missing values of UPCR or eGFR by treatment and stratification factor LN Class to create M=50 imputed datasets with monotone missing patterns. The seed will be set to 55218163 for these MCMC models. In the MCMC model for UPCR imputation, IV methylprednisolone planned total dose at baseline, UPCR values at baseline, Week 13, 25, 37, and 53 will be included as the model input variables. If this model does not converge, the

treatment may be included in the model as an input variable with dose (0, 30, and 60 mg). In the MCMC model for eGFR imputation, IV methylprednisolone planned total dose at baseline, UPCR baseline value, eGFR baseline value and all available post-baseline values up to Week 53 will be included as the model input variables. If there is a model convergence issue, the treatment may be included in the model with dose level (0, 30, 60 mg). If the convergence problem stays, reduction of eGFR post-baseline timepoints will be explored. In this exploration, exclusion of timepoints should be as minimum as possible and timepoints Week 13, 25, 37, and 53 must stay.

In the second step, monotone regression with the predictive mean matching (REGPMM) method will be used to impute the remaining missing values up on the output of 50 datasets with monotone missing patterns from the first step. In the REGPMM model for imputation of UPCR, treatment group and IV methylprednisolone planned total dose at baseline will be included in the model as classification variables. Baseline and post-baseline UPCR timepoints included in the first step imputation will be input variables as well. For eGFR imputation in this step, treatment group and randomization stratifications will be included in the model as classification variables and all timepoints included in the first step will be included in for the imputation of monotone missing. The seed will be set to 81635521.

CRR response at scheduled analysis visits through Week 53 will be defined following the definitions described in Section 3.2.1.

After the completion of imputation, the same statistical method as the primary analysis will be used to analyze each of the 50 complete datasets. The SAS® procedure MIANALYZE will be used to combine the results for the statistical inferences.

8.2.3.3. Sensitivity Analysis using Tipping Point

For the tipping point analyses, let M1 and M2 be the total number of patients with missing CRR assessment at Week 37 in the zetomipzomib and pooled placebo groups, respectively. There are overall (M1+1)*(M2+1) possible ways for imputing missing data as responders or non-responders in this analysis, ranging from imputing all missing values as non-responders to imputing all missing values as responders in each of the two treatment groups. For each of the (M1+1)*(M2+1) different imputation patterns, the same statistical method as the primary analysis will be used for testing statistical significance and the output will be plotted in a rectangle for inspection. The staircase region that separates significant and non-significant outcomes forms the tipping-point boundary.

8.2.3.4. Sensitivity Analysis using FMV-UPCR for missing 24-hour UPCR

Missing CRR and PRR assessments due to missing the 24-hour urine sample data, which is needed to calculate UPCR will be imputed using the calculated UPCR from 2 FMV urine samples for patients in the ITT Population. With this imputed data, the primary and key secondary endpoints will be analyzed and reported.

8.2.4. Subgroup Analysis

For each of the following subgroups, the proportion of patients in the ITT Population achieving CRR at Week 37 will be compared between zetomipzomib and placebo using the CMH test at 2-sided 5% level of significance. Non-responder imputation will be implemented as for the primary analysis in Section 8.2.2 and the same statistics will be presented.

- Average 24-hour UPCR at Screening visit (≤3.0 and >3.0) {stratification factor}
- LN Class (Class III/IV +/- V vs. pure Class V) {stratification factor}
- IV methylprednisolone on Day 1 +/- 7 days (0 to <500 mg, 500-1000 mg, or >1000 to 3000 mg) {stratification factor}
- Maximum MMF dose (≤2 g versus >2 g)
- Age group (\leq 30 years, >30 years)
- Sex at birth as integrated from RTSM (Male, Female)
- Ethnicity (Hispanic or Latino, Not Hispanic or Latino)
- Race (White, Black or African American, Asian, American Indian or Alaska Native, Native Hawaiian or Other Pacific Islander, Other)
- Region (EMEA, Asia Pacific, North America, Latin America)
- Patients who have received IV methylprednisolone within 3 months prior to Screening (Yes/No)
- Current use of MMF or equivalent at the Screening visit (Yes/No)
- Classes of pathology on biopsy (III, III+V, IV, IV+V, Pure V)

If any subgroup contains <5 patients, inferential statistics will be suppressed.

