3. INVESTIGATIONAL PLAN

3.1. Overall Study Design and Plan

[figure not shown]
This is a Phase 2b, randomized, double-blind, placebo-controlled, global, multicenter study to evaluate efficacy and safety of zetomipzomib in patients with active Class III/IV +/-V LN or pure Class V LN described in Figure 1. The study will enroll approximately 279 patients: 249 patients with biopsy-proven Class III/IV +/-V LN with urine protein creatinine ratio (UPCR) ≥1.0 and up to approximately 30 patients with pure biopsy-proven Class V with UPCR ≥2.0. Zetomipzomib or placebo will be administered at a dose level of 30 mg or 60 mg (the latter following step up from an initial Week 1 dose of 30 mg). For each dose group, patients will be randomized in a 2:1 ratio to receive either zetomipzomib or placebo administered as a subcutaneous injection once weekly for 52 weeks, followed by a 4-week safety follow-up visit. Each treatment group (30 mg, 60 mg, or pooled placebo) will include approximately 83 patients per group with Class III/IV +/-V and up to 10 per treatment group with pure Class V LN, for a total of up to 279 patients.

Zetomipzomib or placebo will be administered subcutaneously once weekly starting on Day 1 (Week 1) through Week 52, followed by a safety visit 4 weeks after the last dose of treatment. Zetomipzomib or placebo injections will either be self-administered by the patient/caregiver or via home health service at patient's location, as appropriate, or by study personnel at the investigational site.

During the treatment period, patients will also receive background standard of care therapy consisting of MMF or equivalent for 52 weeks plus oral corticosteroids tapered over 16 weeks. In addition, all patients will also receive intravenous (IV) methylprednisolone on Day 1 (+/- 7 days), unless a patient has had IV methylprednisolone within 3 months prior to Screening or at the Investigator's discretion when a patient has had an inadequate response or adverse effects from prior administration.

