4.2. Sample Size

A sample size of 249 patients with Class III/IV +/-V LN or 83 per treatment group (randomized in a 2:1:2:1 ratio for zetomipzomib 30 mg: placebo: zetomipzomib 60 mg: placebo) will have 80% power to detect a 20% difference (40% versus 20%) in CRR between zetomipzomib and placebo at Week 37 (9 months), using a 2-group binomial test (for pooled estimate of variance) with a 0.05 2-sided α level. The assumption of 20% for CRR in the placebo group was made based on the evaluation of relevant published data (Furie et al., 2020; Rovin et al., 2021).

The sample size calculation is intended for pairwise comparisons for zetomipzomib 60 mg versus the pooled placebo group and for zetomipzomib 30 mg versus the pooled placebo group, respectively. There is no statistical comparison between the 2 zetomipzomib dose groups. This sample size also reflects a planned IA for futility when approximately 50% of the randomized patients with Class III/IV +/-V LN have or would have completed the Week 37 visit with the primary endpoint assessment and prior to the completion of the target study enrollment. Based on the IA findings, sample size (for patients with Class III/IV +/-V LN only) may be increased up to 50%; see Section 11.2 for details.

In addition to the 249 patients with Class III/IV +/-V LN, the study will also enroll up to 30 patients with pure Class V LN across the 3 treatment groups, for a total of up to 279 patients. The 30 patients with pure Class V LN were not included in the power calculation, as well as the assessments for type 1 error and multiplicity.

Approximately 214 sites from ~21 countries worldwide are planned to participate in this study.

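### The CRR subgroup analysis tests each level separately at 5% and has no treatment-by-subgroup interaction test, so a uniform effect can readily look uneven

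*SAP*

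**What the plan says.** SAP 8.2.4 lists 12 subgroup factors. For each subgroup, the proportion achieving CRR at Week 37 "will be compared between zetomipzomib and placebo using the CMH test at 2-sided 5% level of significance". It adds: "Non-responder imputation will be implemented as for the primary analysis in Section 8.2.2 and the same statistics will be presented". In SAP 8.2.2 those statistics are the number and proportion of responders, the weighted difference, the odds ratio with 95% CI, and a p-value. The opening of SAP 8 applies treatment comparisons to each dose against pooled placebo.

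The size rule, "If any subgroup contains <5 patients, inferential statistics will be suppressed", makes sense only if a subgroup is one level of a factor. So the 5% test is run inside every level with at least 5 patients.

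Neither SAP 8.2.4 nor Protocol 10.8.2 mentions a treatment-by-subgroup interaction, an estimate of the difference between levels, or a rule for reading such differences. Two nearby provisions matter. SAP 8.2.2 plans a Breslow-Day test of homogeneity across the randomization strata of the primary analysis. SAP 8.1 treats p-values outside the multiplicity procedure as nominal, a measure of strength of association and not formal hypothesis tests.

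**The concern.** A subgroup analysis asks whether the treatment effect differs between levels. A test inside one level asks whether that level alone reaches p < 0.05, and the answer depends heavily on how many patients the level holds. The trial is sized for about 80% power with all 83 patients per group, so each level has a share of that information and less power.

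A table of within-level p-values invites the reader to set significant levels against non-significant ones and infer that the drug works in some patients and not in others. With a truly uniform effect that contrast is noise. At stake is how the effect is described by region, race, proteinuria stratum, LN Class and the other listed factors. The overall result is not at stake.

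**Working it through.** **Inputs from the SAP.** Section 4.2 plans "249 patients with Class III/IV +/-V LN or 83 per treatment group" and states that this "will have 80% power to detect a 20% difference (40% versus 20%) in CRR between zetomipzomib and placebo at Week 37", "using a 2-group binomial test (for pooled estimate of variance) with a 0.05 2-sided α level". Allocation is 2:1:2:1, so each dose against pooled placebo is 1:1. Section 3.1 gives the one directly stated level size: "up to 10 per treatment group with pure Class V LN".

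**Count of levels in SAP 8.2.4.** UPCR 2, LN Class 2, IV methylprednisolone 3, maximum MMF dose 2, age 2, sex 2, ethnicity 2, race 6, region 4, prior IV methylprednisolone 2, MMF at Screening 2, biopsy class 5. The sum is 34 over 12 factors.

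**Assumptions.** The effect is the same in every level. Splits other than pure Class V are illustrative. The within-level CMH test is treated as single-stratum, because 8.2.4 does not say whether it is stratified further.

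**Step 1: reproduce the plan's power.** Pooled-variance formula, n per arm, p̄ = 0.30:

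power = Φ{[0.20 − 1.96·√(2·0.30·0.70/n)] / √[(0.20·0.80 + 0.40·0.60)/n]}

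For n = 83: (0.20 − 0.1394)/0.0694 = 0.873, and Φ(0.873) = 0.809. This agrees with the stated 80%.

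**Step 2: power within a level at 40% versus 20%.** The exact column enumerates all outcomes of the single-stratum CMH statistic.

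| n per arm | formula | exact |
|---|---|---|
| 83 | 80.9% | 81.4% |
| 41 | 50.7% | 51.1% |
| 20 | 27.6% | 29.1% |
| 10 (pure Class V maximum) | 15.7% | 13.1% |

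**Step 3: chance of a mixed picture for one factor.** Levels hold different patients, so

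P(mixed) = 1 − ∏powerᵢ − ∏(1 − powerᵢ)

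Using the exact powers:

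- 50:50 (42 and 41 per arm): 1 − 0.524·0.511 − 0.476·0.489 = 50%
- 70:30 (58 and 25): 1 − 0.664·0.352 − 0.336·0.648 = 55%
- 80:20 (66 and 17): 1 − 0.715·0.234 − 0.285·0.766 = 61%
- LN Class (83 and 10): 1 − 0.814·0.131 − 0.186·0.869 = 73% (71% with the formula powers)
- three equal levels (28, 28, 27): 1 − 0.361²·0.364 − 0.639²·0.637 = 69%
- four equal levels (21, 21, 21, 20): 1 − 0.282³·0.291 − 0.718³·0.709 = 73%

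**Step 4: smaller true effects, placebo at 20%.** Over the same set of splits, P(mixed) is about 45-57% for a uniform 15-point effect (35% versus 20%) and about 30-38% for 10 points (30% versus 20%).

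**Step 5: what a direct test would do.** A simulated Woolf-type heterogeneity test on the log odds ratio at 5%, with a uniform 40% versus 20% effect, rejects in 4.4% of trials for 42/41 per arm, 3.5% for 66/17 and 2.5% for four equal levels. It signals a difference in no more than about 5% of trials per factor.

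**The case against.** The strongest reply has four parts.

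- **The p-values are nominal.** SAP 8.1 says so, and Protocol 10.8.2 says only that subgroup analyses may be conducted. This limits formal claims and deals with multiplicity. It does not make a within-level test answer the between-level question, and 8.2.4 itself attaches a 5% significance level to it.
- **Effect estimates are already planned.** This stands: every level gets a weighted difference and an odds ratio with 95% CI. What is missing is the comparison between levels. SAP 8.2.2 also ties a CI explicitly only to the odds ratio.
- **There is a homogeneity test.** A reader might infer that the SAP never examines heterogeneity, and the Breslow-Day test shows otherwise. However, it is a joint test across randomization strata. It isolates none of the three stratification factors and leaves out the other nine subgroup factors. Because the primary analysis is confined to Class III/IV +/-V, it cannot compare pure Class V with the rest.
- **The SAP never says that a non-significant level means no effect.** True. The misreading is one that the display invites, not one that the plan adopts.

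A reader might also infer that these results will decide the Phase 3 population. The documents do not say so: Protocol 3.1.2 and SAP 3.1 refer to Phase 3 dose selection, based on efficacy by dose, safety and PK.

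**Conclusion.** The point holds in a limited form. The subgroup analysis tests each level on its own and never tests whether the effect differs between the levels of a factor. At the design effect of 40% versus 20%, uniform across levels and with 83 per group, a given factor shows a mixed picture in about 50% to 73% of trials over the splits examined. A heterogeneity test would signal a difference in at most about 5%.

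It would go too far to say that a uniform effect will usually look uneven, whatever its size. For an even two-level factor the chance is about one in two at 20 points, and for every split examined it is below 40% at 10 points. The figures depend on the assumed level sizes (only the pure Class V maximum is stated directly) and on a single-stratum test within levels. This is a worthwhile improvement to a secondary, nominal analysis. No primary or key secondary inference changes.

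**What to change.** In SAP 8.2.4:

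1. Replace the within-level 5% test by the difference in CRR proportions with its 95% CI for each level, for example in a forest plot.
2. Add one treatment-by-factor interaction test per factor and dose comparison, for example as an added term in the logistic model of SAP 8.2.3.1.
3. State that differential effects are judged from the interaction estimate and not from level p-values.

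The cost is SAP wording and one model term per factor and dose comparison. The downside is that interaction tests also have low power. For a 50:50 factor the standard error of the difference between two level effects is about √(2 × 0.40/41.5) = 0.139, so its 95% CI spans about ±27 percentage points. The interaction result must therefore be read with the CIs, and a non-significant interaction must not be taken as proof of a uniform effect.

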8.3. Key Secondary Efficacy Endpoints

Key secondary endpoints include the proportion of patients achieving the following:

- PRR at Week 37
- CRR at Week 53
- PRR at Week 53
- CRR at Week 25
- PRR at Week 25

Each key secondary endpoint will be analyzed using similar CMH methods as the primary, secondary, and tertiary estimands analyses for the 3 hypotheses stated in Section 8.1. IEs will be assessed through the time point of interest.

Sensitivity analysis 1 to primary estimand: Additionally, each key secondary endpoint will be analyzed using Ge, et. al (Ge et al., 2011) methods similar to the primary endpoint stated in Table 5.

8.4. Other Secondary Efficacy Endpoints

Other secondary efficacy endpoints will be analyzed for the ITT Population (Class III/IV +/- V).

8.4.1. Analysis of Continuous Secondary Efficacy Endpoints

Continuous secondary efficacy endpoints include:

- Percentage change from Baseline in UPCR by visit
- Change from Baseline in clinical Systemic Lupus Erythematosus Disease Activity Index 2000 (SLEDAI-2K) score, excluding complement and anti-dsDNA components
- Change from Baseline in EuroQol 5-Dimension 5-Level (EQ-5D-5L) index score and EQ-VAS of general health.

Observed values of the continuous secondary efficacy endpoints will be analyzed using the longitudinal data analysis method based on a mixed model for repeated measures (MMRM) approach. The model will include fixed effect terms for randomized treatment, visit, and randomized treatment by timepoint interaction. Baseline value will be included as a covariate and the randomization stratification factors will be included as class terms. Within subject error will be modeled by use of an unstructured variance-covariance matrix. If the model does not converge using the unstructured matrix (TYPE=UN), the following variance-covariance structures will be tried in this order until convergence is achieved: Toeplitz (TYPE=TOEP), compound symmetric (TYPE=CS).

Treatment effect (ie, the difference in least-square mean values between each zetomipzomib dose vs pooled placebo and the 2 zetomipzomib doses combined vs pooled placebo) estimates will be extracted from the model by visit along with the associated 95% CIs and 2-sided p-values.

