Continuous efficacy endpoints (ie, change or percentage change from Baseline in UPCR by visit) will be analyzed using the longitudinal data analysis method based on a mixed model for repeated measures (MMRM) approach. This model will include fixed effect terms for randomized treatment, timepoint (ie, visit) and randomized treatment by timepoint interaction. Within subject error will be modelled by use of an unstructured variance-covariance matrix. Baseline value will be included as a covariate and the randomization stratification factors will be included as class terms. Treatment effect (ie, the difference in least-square mean values between

each zetomipzomib dose and placebo and the 2 zetomipzomib doses combined vs placebo) estimates will be extracted from the model by timepoint along with the associated 95% CIs and 2-sided p-values. A sensitivity analysis of this model by using multiple imputation (MI) for handling missing data will be performed. The influence of missing data over time will be assessed using multiple imputation techniques, specifically assuming missing at random and missing not at random (MNAR); for the latter both jump to placebo and tipping point MI analyses will be employed.

The Baseline value for 24-hour UPCR is defined as the average of non-missing 24-hour UPCR results from the Screening visit. Repeat test results will not be used to replace non-missing original test data. When only 1 non-missing sample 24-hour UPCR results from the Screening visit is available, then that single value will be used for the Baseline. Unless specified otherwise, baseline value for eGFR and other parameters including laboratory data is defined as the last value prior to the 1st dose of zetomipzomib or placebo.

In this study, all analyses involving treatment comparisons will be performed based on pairwise comparisons for zetomipzomib 60 mg versus the pooled placebo group and for zetomipzomib 30 mg versus the pooled placebo group. No statistical comparisons will be performed between the 2 zetomipzomib dose groups.

All analyses will be performed in SAS® v9.4 for Microsoft® Windows®.

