#### 10.6.2. Analysis of the Secondary Efficacy Endpoints

The secondary efficacy endpoint analyses will evaluate the proportion of patients treated with zetomipzomib compared with pooled placebo (in pairwise comparison) achieving the following:

- PRR at Week 37
- CRR at Week 53
- PRR at Week 53

- CRR at Week 25
- PRR at Week 25
- Percentage change from Baseline in UPCR by visit
- Time to CRR
- Time to PRR
- Time to death or renal-related events
- Proportion of patients achieving CRR (at Weeks 25, 37, and 53) with successful taper of prednisone or equivalent to ≤5 mg by Week 17
- Proportion of patients achieving CRR (at Weeks 25, 37, and 53) with no use of prednisone or equivalent during the 8 weeks prior to the renal response assessment
- Proportion of patients with UPCR ≤0.5 at Weeks 13, 25, 37, and 53
- Proportion of patients achieving CRR with UPCR ≤ upper limit of normal (ULN) at Weeks 25, 37, and 53
- Change from Baseline in clinical Systemic Lupus Erythematosus Disease Activity Index 2000 (SLEDAI-2K) score, excluding complement and anti-dsDNA components.
- Change from Baseline in EuroQol 5-Dimension 5-Level (EQ-5D-5L)

Time to death or renal-related events is defined as the first event occurring among the following:

- 1. Death
- 2. Doubling of serum creatinine
- 3. Proteinuric flare
- 4. Renal event-related treatment failure

The primary analysis of certain key secondary endpoints (ie, CRR at Week 53, PRR at Week 37 and Week 53) will follow the primary estimand principle, using the same approach as described in Section 10.6.1 and Table 6.

For a continuous endpoint such as percentage change from Baseline in UPCR by visit, data will either be observed or missing (ie, no NRI will be applied). The missing data will be handled by the following 2 approaches: (1) using MMRM model and (2) using MI to impute missing data and then applying MMRM model for analysis. The MMRM model (ie, Approach #1) will be the primary analysis method.

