8.5.1. Analysis of Continuous Exploratory Endpoints

Continuous exploratory endpoints include:

- Change from Baseline in antibodies (anti-dsDNA antibody, C1q autoantibody)
- Change from Baseline in complement (C3, C4)
- Change from Baseline in 24-hour urine protein
- Change from Baseline in serum albumin
- Change from Baseline in serum creatinine
- Change from Baseline in eGFR
- Change from Baseline in serum lipids (serum low-density lipoprotein [LDL] cholesterol, serum total cholesterol, serum triglycerides)

- Change from Baseline in blood hemoglobin A1c (HbA1c)
- Change from last visit in the GTI as measured by the GTI-CWS and the GTI-AIS
- Change from Baseline in SLEDAI-2K
- Change from Baseline in 28-joint counts (both tenderness and swelling counts)
- Change from Baseline in PGA score
- Change from Baseline in renal biopsy histopathology and immunohistopathology (optional; analysis of these endpoints is outside the scope of this SAP)
- Change from Baseline in IgM, IgG, and IgA

The continuous exploratory endpoints will be analyzed using similar MMRM methods as the main analysis of the continuous secondary efficacy endpoints. No MI analysis will be conducted for the continuous exploratory endpoints. Log-transformed values may be used for laboratory endpoints that are skewed and not normally distributed (eg, serum creatinine).

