9. SAFETY ANALYSIS

All summaries of safety will be performed for the Safety Population using descriptive statistics, unless otherwise noted. All safety data will be listed for the Safety Population.

Safety assessments will include AEs, clinical laboratory tests, vital sign measurements, physical examinations, weight, 12-lead electrocardiogram (ECG), urine pregnancy testing, and hepatitis B DNA assessments (for HBcAb-positive patients only).

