9.2. Clinical Laboratory Evaluations

Clinical safety laboratory panels include hematology, serum chemistry, immunoglobulins (IgG, IgA, IgM), urinalysis, and coagulation. See Appendix 12 for a list of the clinical safety laboratory tests within each panel.

All clinical safety laboratory tests will be performed by the central laboratory according to the Schedule of Assessments (Appendix 1). Additional tests may be performed locally at any time during the study as determined necessary by the investigator; these data will be listed only and will not be included in summaries.

For continuous results, mean of the observed result, mean change from baseline (post-baseline visits only), and median change from baseline (post-baseline visits only) will be summarized for each scheduled visit. Standard deviation, median, interquartile range, minimum, and maximum will be presented. Additionally, last post-baseline value as well as maximum and minimum post-baseline values (through last safety follow-up visit and including unscheduled visits) and corresponding changes from baseline will be presented. For clinical laboratory measures that are not normally distributed per the Shapiro-Wilk test, the endpoint will be log-transformed when using MMRM methods or non-parametric test to assess change from baseline.

For qualitative results, the number and proportion of patients in each category will be summarized by scheduled visit.

As applicable, analysis of laboratory data will be based on SI units. For NCI-CTCAE gradable parameters, tables summarizing shift in NCI-CTCAE grades from baseline to each scheduled post-baseline timepoint, to last post-baseline assessment, and to worst post-baseline assessment (scheduled or unscheduled) will be displayed in cross-tabulations. For parameters with toxicity grading in both directions (high and low), shift will be presented separately for high and low.

For non-gradable parameters, tables summarizing shift in normal/abnormal classification from baseline to each scheduled post-baseline timepoint will be displayed in cross-tabulations. For parameters with normal/abnormal classification in both directions (high and low), shift will be presented separately for high and low.

For lab parameters, a graph of mean change from baseline (+/- SD) and/or median change from baseline (IQR) over time will be presented by treatment group.

All lab results will be listed by panel. Local lab results will be clearly identified on the listings.

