- The protocol Section 10.6.1, states: "Supplemental analyses on the primary and selected key secondary endpoints may be performed using logistic regression models. These analyses will include covariates for treatment, UPCR at baseline (stratification factor), biopsy class, IV methylprednisolone use at Baseline (stratification factor), and region and other selected baseline parameters." However, in the SAP, Section 8.2.3.1 we specify that the baseline 24-hour UPCR value (as a continuous number) will be used instead of the categorical strata factor by stating: "The model will include covariates for treatment, stratification factors (LN Class, IV methylprednisolone), baseline 24-hour UPCR value (as a continuous number, not a stratification factor), and geographic region."

- Added 3 new exploratory endpoints to the SAP which were not included in the Protocol:
 - Time to antibodies normalization or negative status (anti-dsDNA antibody normalization, anti-C1q antibody negative status)
 - Time to complement (C3, C4) no longer being low
 - Change from Baseline in IgM, IgG, and IgA
- It should be noted that there is no reference to the sponsor's Steering Committee (SSC) in the SAP because Kezar has decided not to form and include a SSC in this study.
- The following analytes have been added to Table in Appendix 12:
 - neutrophil count
 - Anti-dsDNA
 - Complement (C3 and C4)
 - C1q autoantibody
 - Quantitative immunoglobulins (immunoglobulins M, G, and A)
 - white blood cells
 - red blood cells
 - 24-hour UPCR
 - FMV UPCR
 - 24-hour Proteinuria (Urine Protein (24hr))

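### Step 1 of the multiple imputation in SAP 8.2.3.2 can draw negative UPCR values that pass the CRR threshold; under plausible UPCR distributions the imputed patients pull the arms together

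*SAP*

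**What the plan says.** **Imputation (SAP 8.2.3.2).** UPCR and eGFR are imputed separately, and CRR is then derived from the imputed values. Step 1 uses MCMC, by treatment and LN class, to fill intermediate gaps and leave 50 data sets with monotone missingness. The UPCR inputs are planned IV methylprednisolone dose and UPCR at baseline and Weeks 13, 25, 37 and 53. No transformation, minimum or truncation is stated. Step 2 fills the remaining gaps by predictive mean matching.

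**CRR (SAP 3.2.1.1).** UPCR at or below 0.5 with no lower limit, plus an eGFR condition.

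**Primary analysis (SAP 8.2.2).** Missing CRR at Week 37 counts as non-response, so the imputation is a sensitivity analysis.

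**Continuous UPCR endpoint.** SAP 8.4.1 lists "Percentage change from Baseline in UPCR by visit", models observed values by MMRM, and gives the effect measure as "the difference in least-square mean values between each zetomipzomib dose vs pooled placebo and the 2 zetomipzomib doses combined vs pooled placebo". Protocol 10.6 has "Continuous efficacy endpoints (ie, change or percentage change from Baseline in UPCR by visit) will be analyzed using the longitudinal data analysis method", and Protocol 10.6.2 adds "The MMRM model (ie, Approach #1) will be the primary analysis method". Elsewhere, SAP 9.2 says that for laboratory measures "not normally distributed per the Shapiro-Wilk test, the endpoint will be log-transformed when using MMRM methods", or a non-parametric test is used. Its test list in Appendix 12 includes 24-hour UPCR, one of the additions recorded in SAP 13 under "The following analytes have been added to Table in Appendix 12". SAP 8.5.1 says of exploratory endpoints: "Log-transformed values may be used for laboratory endpoints that are skewed and not normally distributed (eg, serum creatinine)".

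**The concern.** MCMC imputation of this kind draws from a multivariate normal distribution. UPCR is positive and likely to be right-skewed. A normal model with the same mean and SD puts probability below zero, and it misplaces the share below 0.5. An impossible negative value then satisfies the UPCR half of CRR. The size and direction of the error depend on the true response rate, so it need not cancel between arms. A check meant to show that the primary result is robust to missing data would then carry a bias of its own.

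**Working it through.** **Anchor.** The plan states 83 per group and 80% power for 40% vs 20% (SAP 4.2). With pooled variance, SE under the null = √(2×0.3×0.7/83) = 0.0711, and SE under the alternative = √((0.2×0.8+0.4×0.6)/83) = 0.0694. Then (0.20 − 1.96×0.0711)/0.0694 = 0.873, giving power 80.9%. The stated figure reproduces, so 83 per arm and the rates 20% and 40% are used below. Every UPCR spread, correlation and gap rate is an assumption.

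**Direction, in closed form (covariates ignored).** Match a normal distribution to a skewed UPCR by mean and SD.

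- P(draw < 0) = Φ(−1/CV). For a lognormal, CV = √(exp(s²) − 1), so log SD s = 0.6 / 0.9 / 1.1 gives 6% / 19% / 26%. For a gamma of shape k, CV = 1/√k, so k = 3 / 1.5 gives 4% / 11%.
- Lognormal, s = 0.9, true share 20%: median = 0.5×exp(0.842×0.9) = 1.07, mean = 1.60, SD = 1.79. P(draw ≤ 0.5) = Φ((0.5 − 1.60)/1.79) = 27%.
- Same s, true share 40%: median 0.63, mean 0.94, SD 1.05. P(draw ≤ 0.5) = Φ((0.5 − 0.94)/1.05) = 34%.

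The true difference of 20 points becomes about 7 among imputed values.

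**Simulation.** Week 37 UPCR was imputed by Bayesian normal regression on baseline and Weeks 13, 25 and 53, within arm, 83 per arm, 1,500 trials per cell. This is equivalent to the MCMC draw when only Week 37 is missing. With 8% gaps at random, between-visit correlation 0.5 / 0.7 / 0.85 and baseline median 2.5, selected cells were:

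| Assumed UPCR | Correlation | Negative draws (true 20% / 40%) | Share ≤0.5, true 20% | Share ≤0.5, true 40% |
|---|---|---|---|---|
| Lognormal, log SD 0.6 | 0.5 | 5.3 / 5.5% | 22.3% | 34.3% |
| Lognormal, log SD 0.9 | 0.5 | 16.3 / 16.7% | 26.1% | 34.6% |
| Lognormal, log SD 1.1 | 0.5 | 22.4 / 21.5% | 28.9% | 33.9% |
| Gamma, shape 1.5 | 0.5 | 9.9 / 10.9% | 20.1% | 34.5% |
| Gamma, shape 3 | 0.85 | 1.2 / 1.3% | 19.5% | 38.1% |

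A second set (10% gaps, correlation 0.5 and 0.7, log SD 0.6–1.2, gamma shape 1.2–3) gave 6–27% (lognormal) or 5–16% (gamma) negative draws. Shares were 23–30% or 21–24% for a true 20%, and 34–36% or 33–36% for a true 40%.

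**Shrinkage per imputed gap.** Subtract the imputed difference from the true one. Lognormal 1.1, correlation 0.5: (39.6 − 19.7) − (33.9 − 28.9) = 14.9 points. Most cells lie between 5 and 15 points. The mildest (gamma shape 3, correlation 0.85) gives (40.0 − 19.8) − (38.1 − 19.5) = 1.6 points.

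**Effect on the overall difference** = gap rate × shrinkage. For 5–15 points per gap:

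| Gap rate (assumed) | Overall shift, points |
|---|---|
| 2% | 0.1–0.3 |
| 5% | 0.25–0.75 |
| 10% | 0.5–1.5 |

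**Which gaps reach step 1.** A Week 37 gap is intermittent only if Week 53 is observed. The primary analysis takes place when all Class III/IV ± V patients have reached Week 37. Week 53 is 16 weeks later, so under uniform recruitment the share for whom it is due is 1 − 16/recruitment weeks: 69% / 85% / 90% for 12 / 24 / 36 months (assumed). This scales the Week 37 shift down further.

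**Alternatives in the same simulations.** Log-scale draws are never negative. They give 19–21% and 39–41% under lognormal, and 20–23% and 41–45% under gamma. Predictive mean matching with 5 donors gives 19–21% and 40–41% under both.

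**The case against.** The strongest reply is that the effect is very small and well covered elsewhere. Protocol 7.2.2.2 suggests replacing a missed 24-hour collection within 4 weeks, and SAP Table 3 extends the Week 37 window to Day 281, so intermittent gaps should be few. SAP 8.2.3.4 substitutes first-morning-void UPCR. SAP 8.2.3.3 runs through every responder/non-responder allocation without modelling UPCR. A negative draw meets only the UPCR half of CRR, because eGFR must also qualify. All of this stands and limits the size. It does not make the step sound, and the repair is cheap.

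A reader might infer that negative draws simply inflate response. They do not. The share is too high or about right near 20% (under gamma almost unbiased there) and too low near 40%.

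A reader might also infer that the scale of the 8.4.1 analysis is unsettled, or should be changed to log. The documents do not support that. SAP 8.4.1 and Protocol 10.6.2 fix percentage change and MMRM. The 9.2 rule sits in the safety section, where "All summaries of safety will be performed for the Safety Population using descriptive statistics, unless otherwise noted" applies; it offers a non-parametric test as an alternative; and a percentage change, negative for every improver, cannot be logged. The 8.5.1 option covers exploratory endpoints only. Nor is log uniformly better. In a single-visit stand-in for the MMRM at 20% vs 33% response, raw against log power was 78 vs 86% to 52 vs 78% under lognormal residuals (log SD 0.6 to 1.2), but 91–94 vs 84–87% under gamma. Neither scale inflated type I error, and the endpoint's p-values are nominal (SAP 8.1).

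**Conclusion.** The imputation point holds and is minor. As written, step 1 can produce impossible UPCR values that pass the UPCR criterion, and under the distributions tried the imputed patients understate the arm difference. The shift is about 0.1–1.5 points, less in the mildest gamma case and less again where Week 53 is not yet due. It rests on assumed skewness, correlation and gap rates and on gaps missing at random, and it concerns the UPCR part of CRR only.

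The primary analysis, the tipping-point grid and the futility and sample-size rules do not use these draws. Step 2 creates no new negative values, although it could reuse a step-1 negative as a donor. Protocol 10.6.4 also names multiple imputation for key secondary endpoints, while SAP 8.3 does not list it. If it is run there, CRR at Week 25 meets the same step whenever Week 37 is observed.

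On 8.4.1 only a clarification is due: the long laboratory list in Appendix 12 makes the reach of the 9.2 rule easy to misread.

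**What to change.** 1. In SAP 8.2.3.2, impute log(UPCR) in both steps and exponentiate before deriving CRR. Alternatively, fill the intermittent gaps by predictive mean matching, which needs no distributional shape and is already programmed for step 2.
2. In SAP 8.4.1, state that the Shapiro-Wilk rule in 9.2 does not decide the scale of this endpoint. An MMRM on the log ratio to baseline could be added as a supportive analysis. Replacing percentage change as the main scale is not required.

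The cost is SAP wording and a small programming change, with no new data. If the UPCR tail is light, log-scale draws overshoot by about 1–5 points per imputed value; predictive mean matching avoided this in the cases tried.
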